# PROVISIONS TO MONITOR THE DATA TO ENSURE THE SAFETY OF PARTICIPANTS:

Not applicable, as the study procedures pose no more than minimal risk of harm to participants.

#### WITHDRAWAL OF PARTICIPANTS:

There are no planned circumstances under which subjects will be withdrawn from research without their consent. Notably, as the study at all phases is of minimal harm to participants, there are no safety reasons that would necessitate withdrawal. However, if participants request withdrawal from the study for any reason, their participation would be discontinued immediately. If participants request termination of their participation, they will be instructed (in the consent form) to contact [name]. Upon receiving this request, they will be immediately withdrawn and no further prospective data will be collected. Data collected prior to withdrawal will be maintained and analyzed unless requested otherwise. The only administrative reason for

withdrawal of participants is loss to follow-up; if a focus group participant fails to present for the scheduled focus group, or if an individual testing patient fails to interact with SweetMama for the duration of participation (2 weeks), she will be considered lost to follow-up. If a pilot RCT participant fails to interact with the research team for the scheduled "check-ins" for 2 months or more, she will be considered lost to follow-up.

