# **STUDY TIMELINES:**

Focus groups and individual user interviews: Women recruited to the focus groups and individual user interviews will have approximately 1 hour of study participation in which they will be asked to provide feedback about SweetMama while testing it and discussing its potential use during pregnancy. They will not be followed longitudinally.

Longitudinal individual testing: Women recruited to the longitudinal usability testing phase of SweetMama will actively participate for two weeks, during which time they will have frequent contact with the study team. After this period of active use, we will request patient permission to follow up their pregnancy outcomes via record review, but we will not require further information nor study participation.

Provider testing: Health care providers recruited to a focus group or individual interview will have approximately 1 hour of study participation in which they will be asked to provide feedback about SweetMama while testing it and discussing its potential clinical use. Participation in the study will be over at the end of the focus group or interview.

Pilot RCT: Women recruited to the pilot RCT phase of SweetMama will enroll in the study upon initiation of prenatal care for diabetes, which could be early in pregnancy at the time of first prenatal visit, or at a later point if they have transferred care to this site. Women will actively participate for the duration of their pregnancy and postpartum period, which could be as long as 44 weeks (for example, of a woman enrolled at 6 weeks, delivered at 40 weeks, and continued through 10 weeks), or could be as few as 20 weeks (if enrolled at

30 weeks and delivered at 40 weeks). We will follow their patient-reported and medical record outcomes throughout this time period. We will not require further information or study participation after the postpartum exit interview. Health care providers who participate in the provider survey will complete a one-time survey at the time of their patients' enrollment and another survey upon exit; the exit survey will be repeated for each patient they have who is enrolled in the pilot trial. Healthcare providers will additionally complete a one-time in-depth interview after they have had enrolled patients complete their participation.

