# Feasibility testing: Pilot RCT (patient component)

After SweetMama is modified based the usability testing phase and provider feedback, which we anticipate will take 1-2 months, feasibility testing will occur with up to 50 eligible pregnant women via field testing. The goals of this phase are to field test recruitment, retention, and assessment strategies, as well as delivery of SweetMama within a pilot RCT, to assess feasibility and inform the design of a full trial assessing behavior, glycemic control, and perinatal outcomes. We will collect feasibility data regarding recruitment, technical challenges, quality assurance, and retention, as well as clinical outcomes data and patient-reported outcomes.

Women will be recruited to participate in the same manner as described above, via routine clinical interactions. Medical records will be reviewed for eligibility and women with diabetes will then be approached for verbal in-person screening and recruitment using a recruitment script (Appendix E). Participants will sign written informed consent. Enrolled women will be provided a "SweetMama timeline" document that explains the study activities, provides contact information, and outlines how to contact the team for technical help or any other needs. We will then randomized participants. Randomization, via REDCap, 76 will be unbalanced to

offer greater odds of receiving the experimental treatment in order to enhance the research team's experience with SweetMama and incentivize participation, with a target sample of 40 (randomized 1:3, stratified by DM type). The target sample size is 40, but up to 50 women may be enrolled in order to account for drop-out or the requirements of the randomization schema.

Women who are randomized to usual care will receive no orientation to or enrollment in SweetMama. They will receive surveys at enrollment, during the delivery hospitalization, and at the postpartum visit (see details in table below). Women who receive usual care will not undergo interviews.

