Women who are randomized to SweetMama testing will be oriented to SweetMama use on their own Apple or Android-based phones. Once enrolled, with the support of trained research staff, participants will undergo standardized orientation to SweetMama using the introductory video developed in the usability phase. The SweetMama introductory video will be updated between the usability and feasibility testing phases. The training of the research team to perform standardized orientation and support enhances the fidelity of the intervention. Women will then use SweetMama throughout pregnancy. The curriculum delivery will be performed as described above and will be automated based on entry gestational age. Their appointment reminders will be entered into the researcher dashboard prior to appointments, and their goal messages will be set via involvement of the clinical team at appointments as recommended by the APN. If a woman starts her participation already on insulin, she will receive the supplementary insulin curriculum from enrollment; if she initiates insulin after enrollment, she will initiate the insulin curriculum that week. SweetMama users will undergo every 2-week check-ins for technical and quality assurance; these brief check-ins will take place via text, phone, email, or in-person, depending on participant preference. Use of SweetMama will continue until the completion of the postpartum visit, with a curriculum that extends through postpartum week 8. They will receive surveys at enrollment, during the delivery hospitalization, and at the postpartum visit (see details in table below). SweetMama participants will also undergo a brief 2-part exit interview (see below) focusing on feedback for SweetMama use, areas for improvement and how SweetMama affected their engagement. The primary interview will take place during the delivery hospitalization or shortly thereafter if not feasible at the time; a brief follow-up interview focusing on the postpartum curriculum will occur at the postpartum visit.

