- Treatment adherence, measured as 1) retention in clinical care with completion of all recommended selfcare measures (visits attended and with glucose data available), and 2) proportion of glucose values out of range when presenting to care
- Maternal and neonatal outcomes, including glycemic control (Appendix A)

For the SweetMama arm, we will collect unique data on:

- Quality assurance and technical functioning: At each technical check-in point, we will complete a short standardized check-in regarding any errors, technical problems, or content clarifications. In this field testing phase, the 2-item quality assurance check-in will be completed by completion of a brief mobile REDCap survey.
- Interview Semi-structured interview framed by the Health Belief Model on experiences with SweetMama. Information will be designed to elicit feedback about technical problems, ease of use, satisfaction abd overall usefulness for various components of SweetMama (see Appendix F)
- Satisfaction measured via the System Usability Scale (SUS).
- Satisfaction and usability measured via the Usefulness, Satisfaction and Ease of Use (USE)
   Questionnaire
- User interaction data client event data will be identical to data in the usability phase.

[figure not shown]
As in the usability phase, only data related to how and when SweetMama is used will be collected and the format in which it is stored will contain no identifying information about users. Furthermore, the information saved on the server will only be accessible to people provided with the proper credentials (members of the research team, research collaborators, and the users themselves). All study activities will take place within Northwestern Medicine, specifically in the PAC clinic, General Obstetrics/Gynecology practice, and Maternal-Fetal Medicine practice. No physical procedures will be performed and there are no specific procedures used to monitor participants for safety or minimize risks, as this poses no more than minimal risk to participants. Source records for the study include interviews, surveys, and chart data, as described above. All questionnaires will be collected using REDCap. The study has been updated in clinicaltrials.gov per requirements.

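### The pilot RCT's only loss-to-follow-up rule runs on check-ins that the text schedules only for SweetMama users, and no common retention criterion overrides it

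*Combined protocol and SAP*

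**What the plan says.** All references are to the current protocol in the combined file.

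- **WITHDRAWAL OF PARTICIPANTS.** The only administrative reason for "withdrawal of participants is loss to follow-up". For the pilot, the rule applies when a participant, with no arm named, "fails to interact with the research team for the scheduled 'check-ins' for 2 months or more, she will be considered lost to follow-up".
- **Feasibility testing: Pilot RCT (patient component), SweetMama arm.** "SweetMama users will undergo every 2-week check-ins for technical and quality assurance". The data list that opens "For the SweetMama arm, we will collect unique data on" includes this item: "At each technical check-in point, we will complete a short standardized check-in regarding any errors, technical problems, or content clarifications". The outcomes table also puts technical check-ins in the SweetMama column.
- **Same section, usual care.** These women get no orientation to the app and no interviews. "They will receive surveys at enrollment, during the delivery hospitalization, and at the postpartum visit".
- **STUDY TIMELINES.** Pilot participation is a period "which could be as long as 44 weeks" (enrolled at 6 weeks, delivered at 40, followed for 10 more), or it "could be as few as 20 weeks" (enrolled at 30 weeks).
- **Retention.** It is a primary outcome with a target of at least 80%. The outcomes table lists it for all women, monthly and at delivery, as continuing in care and in the protocol. The list below the table mentions only continuing in the protocol, with study and medical records as the source. The quantitative analysis plan reports retention cumulatively and by month, compares it between groups, models it on SweetMama use and sets the 80% target. It does not say whether the target applies to the whole sample or to one arm.

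**The concern.** The withdrawal rule is worded for every pilot participant, but its trigger exists in one arm only. A SweetMama woman who stops answering technical check-ins can be administratively withdrawn even if she attends her visits and would complete the delivery and postpartum surveys. A usual-care woman with the same behaviour cannot be.

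The retention wording does not resolve this. It gives a label, a source and a schedule, but it names no survey, visit, contact or time window, and its two forms differ on whether continuing in care counts. The check-in rule is the only pilot text that turns non-contact into a status, so an analyst deciding who has continued in the protocol could reasonably turn to it.

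At stake is the retention estimate that the pilot exists to provide for the full trial. A difference between arms, or a SweetMama figure under 80%, could then partly reflect skipped technical check-ins.

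**Working it through.** The plan has no power or retention calculation to reproduce; the sample-size section says that none was made. The check therefore covers contact counts and the size of the possible effect.

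**Inputs from the documents.** Target 40, randomised 1:3; check-ins every 2 weeks; participation 20 to 44 weeks; delivery taken at 40 weeks and follow-up to 10 weeks postpartum, as in the timeline examples.

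**Assumptions (the documents give no values).** Miss rate q per check-in of 20%, 30% or 40%, independent between check-ins; delivery and postpartum visits always attended and counted as contacts.

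**Arm sizes.** 40 × 3/4 = 30 SweetMama; 40 × 1/4 = 10 usual care.

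**Contacts between enrolment and delivery.** The interval is 40 − 30 = 10 weeks to 40 − 6 = 34 weeks. The text schedules no research contact for a usual-care woman in that interval.

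**Misses needed.** Two months is 2 × 365.25/12 = 60.9 days. Counting from the last contact, misses at days 14, 28, 42 and 56 leave a gap to day 70, which exceeds 60.9. Three misses leave a gap of 56 days, which does not. So four consecutive misses suffice. The rule does not say when the clock starts. Counted from the first missed check-in, five would be needed and the chances below would be lower.

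**Check-ins between contacts.** A 10-week stretch has check-ins at weeks 2, 4, 6 and 8, so 4. A 34-week stretch has 16, at weeks 2 to 32. The shortest participation is therefore 4 + 4 and the longest 16 + 4.

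**Chance of at least one run of four misses.** Let a(n) be the chance of no such run in n check-ins, with a(0) to a(3) equal to 1 and

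a(n) = (1 − q)[a(n−1) + q·a(n−2) + q²·a(n−3) + q³·a(n−4)].

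For n = 4 this gives 1 − a(4) = q⁴. The chance over both stretches is 1 − a(first)·a(second).

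| q | 1 − a(4) | 1 − a(16) | 20 weeks (4 + 4) | 44 weeks (16 + 4) | Usual care |
|---|---|---|---|---|---|
| 20% | 0.0016 | 0.0169 | 0.3% | 1.8% | 0 |
| 30% | 0.0081 | 0.0749 | 1.6% | 8.2% | 0 |
| 40% | 0.0256 | 0.2002 | 5.1% | 22.1% | 0 |

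Without resetting at delivery, uninterrupted chains of 10 and 22 check-ins would give 0.9/4.2/11.7% and 2.4/10.7/27.6%. The lower figures suit the women of interest, because a completer has by definition been seen at delivery.

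**Effect on retention.** One completer classed as lost costs 1/30 = 3.3 points in the SweetMama arm and 1/40 = 2.5 points overall. If true retention is R in both arms and a share g of retained SweetMama women is reclassified, the expected difference is −R·g. At an assumed R = 0.90:

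| g | SweetMama retention | Difference | Chance of 24/30 or more |
|---|---|---|---|
| 0 | 90.0% | 0 | 97% |
| 5% | 85.5% | −4.5 points | 87% |
| 10% | 81.0% | −9.0 points | 66% |
| 20% | 72.0% | −18.0 points | 22% |

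**Precision for scale.** 8/10 against 24/30 is a difference of 0 with a Newcombe 95% CI of −33 to +22 points. Even 10/10 against 24/30 gives Fisher p = 0.31.

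**The case against.** The best reply is that the check-in rule governs withdrawal, not retention. Neither the outcomes section nor the analysis plan cites it, and nothing says that a woman lost to follow-up is a woman not retained. Retention has a source and a schedule shared by both arms, and neither depends on check-ins. That stands, so the effect on the outcome is conditional. It does not remove the problem, because a shared source and schedule do not tell the analyst what makes a woman retained, and no text says that an administratively withdrawn woman still counts.

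The usual-care contact schedule is also not fully visible. The payment text mentions four time points but lists three, a pilot figure is not shown, and the timeline document given to enrolled women is not included. A usual-care check-in cannot be excluded, but the text describes none.

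A reader might infer more: that retention is unmeasured in usual care, so that drop-out there goes unseen and the usual-care or pooled figure is inflated. The documents do not support this. Missed delivery and postpartum surveys would be visible, all patients deliver at one hospital, the clinic's patients are described as well known to staff, and payments are tied to these contacts.

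Finally, the miss rates are assumed, the effect may be less than one woman, and the study is declared not to be hypothesis-testing. All true, and they limit the consequence.

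**Conclusion.** The mismatch is certain on the visible text: a rule written for all pilot participants can operate only in the SweetMama arm, and no criterion for the primary retention outcome overrides it. That it distorts retention is conditional on loss-to-follow-up status being used to decide who continued in the protocol, which the documents neither state nor rule out. If it is used, the between-arm comparison is biased against SweetMama, and SweetMama-arm retention may be lowered against the 80% target.

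The size cannot be fixed from the documents. Under the stated assumptions the chance per SweetMama woman runs from 0.3% (20 weeks, 20% missed) to about 22% (44 weeks, 40% missed), and each completer affected costs 3.3 points in an arm of 30. A reader might infer that a significance test would mislead; with 30 against 10 women and no hypothesis test intended, the harm is to a pilot estimate. It should still be fixed, because that estimate informs the full trial and the repair is cheap.

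**What to change.** 1. Define study retention identically in both arms among all randomised women, including any enrolled beyond 40. Use completion of the postpartum survey within a stated window as the main measure and completion of the delivery survey as a second. Report chart-based retention in care separately.
2. State one classification for pregnancies that end early, since enrolment is allowed from 6 weeks.
3. State whether the 80% target is pooled or per arm. Report retention overall and per arm with exact 95% CIs. At 80% observed these are 64-91% for 32/40, 61-92% for 24/30 and 44-97% for 8/10.
4. Limit the check-in sentence to SweetMama users. Say that it neither determines retention nor stops collection of the delivery and postpartum surveys; the section ends prospective collection on a woman's request and is silent for administrative withdrawal. Report check-in response as a SweetMama process measure.
5. Base any between-arm monthly figure only on sources applied equally in both arms, such as attended care in the chart. Staff contact would not do, because 2-weekly contact would reveal departures sooner in one arm.

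The cost is wording in the withdrawal, outcome and analysis sections. Both surveys and retention in care are already collected, so no new data are needed. The downside is that drop-out is dated less precisely, and stated retention may be slightly lower because a woman who completes only the delivery survey counts as not retained on the main measure.

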#### **RISKS TO PARTICIPANTS:**

Breach of confidentiality is a risk associated with this research, although all survey data will be maintained on a HIPAA complaint online database or stored in a locked, on-campus secure office. Additionally, in this phase, participants may be asked to use their own phone and data plans; patients who do not have unlimited data may experience either data charges or find that SweetMama is inaccessible until they are on WiFi. Extensive efforts will be made to orient subjects to SweetMama and help them reduce the risk of unanticipated data charges.

The participants are otherwise not subject to any risks from the intervention testing process or chart reviews. If participants feel increasing stress from participation, they may choose to terminate participation. The likelihood of discomfort from this study is very low, given that the study is focused on their perspectives on a health behavioral intervention.

There will be no effect on the woman's medical care, and there are no medical interventions in this study. There are no pregnancy-specific risks to the pregnant woman or her fetus due to participation in this survey study. No study-specific procedures have risks to subjects that are currently unforeseeable.

There are no risks to others who are not participants.

Health care provider participants in focus groups will be subject to minimal risk. Participants will not be asked any questions about their own personal health. All questions to health care providers/clinic staff will be about their experiences with patients and their opinions of SweetMama. Thus, few risks are anticipated aside from breach of confidentiality as described above. As above, provider participants will also be able to terminate participation at any time. There will be no effect of participation on the individual's employment or medical care.

## **POTENTIAL BENEFITS TO PARTICIPANTS:**

The goal of this study is to develop a supportive health behavioral intervention that improves maternal outcomes in the setting of diabetes during pregnancy. It is possible that some women may find the completion of the focus group or user interview interesting and it may provoke further discussions with their clinician; however, no clinical benefits are anticipated. Their involvement will hopefully improve the quality of care for future patients.

However, we do anticipate that the 2-week individual testing period and the pilot RCT may offer some benefits to patients who are using SweetMama; namely, we are offering a supportive and educational program that provides women information and other psychosocial support during a pregnancy complicated by diabetes. We do not believe there will be long term perinatal benefits with just this short period of participation (usability testing phase) or in the small population of the pilot RCT phase (feasibility testing), but

we do anticipate that participation in SweetMama testing may enhance the woman's knowledge, motivation, or engagement in care.

#### **VULNERABLE POPULATIONS:**

Pregnant women are the primary focus of this investigation. This study would not be possible in a non-pregnant population, as the goal is to assess the relationships described in the context of pregnancy. Women will be approached in the clinic setting, when they are not in pain and when they are medically stable. They will not undergo any medical procedures. Survey procedures do not involve more than minimal risk to pregnant women. There is no risk to the fetus or newborn. Careful attention will be paid to ensuring that all women are provided confidential study participation and that their PHI is carefully protected. Women are not asked to undergo any interventions or procedures, and their medical care will not be affected by study involvement. The checklist HRP-412 has been reviewed.

This study does not involve research with neonates of uncertain viability, nonviable neonates, prisoners, minors, or cognitively impaired adults.

